Experimental sessions during caffeine maintenance. After receiving caffeine maintenance for at least one week, participants will continue daily caffeine administration and will also be exposed to experimental test sessions across approximately 3-4 weeks (one session each for placebo, 1, 2, 3 and 4 mg/70 kg nicotine and 300 mg caffeine). The purpose of the nicotine sessions is to assess the subjective and reinforcing effects of nicotine, whereas the purpose of the caffeine session is as a manipulation check to test tolerance to caffeine during caffeine maintenance relative to placebo maintenance. The order in which the different doses for experimental sessions are received will be counterbalanced across participants. Subjects will report to the laboratory approximately 2-3 times per week, depending on schedule considerations. Sessions will be separated by at least 48 hours (e.g., Monday, Wednesday, Friday sessions). At each visit, participants will provide a saliva sample, complete pre-drug subjective questionnaires, and orally ingest study capsules with water under double-blind conditions. After leaving the laboratory, outcome measures will be assessed at 1, 2, 3, and 4 hours post-capsule administration.

Measures will include subjective ratings of drug effects (e.g., energetic, drowsy/sleepy, elated, jittery/shaky) and surrogate measures of reinforcement such as liking, take again, and the multiplechoice reinforcement procedure, which we have used in previous research. These questionnaires will be completed online using Qualtrics survey technology, including via the Qualtrics App while in the laboratory, or using conventional paper forms. When participants are completing their surveys online, a survey link will be sent to them via email or text message. Paper forms of surveys will be provided as a back-up in the event of technical issues with administering surveys via Qualtrics, in the event of difficulties with participant compliance for online assessments, or in the event the participant does not have a smart phone or computer access. The multiple-choice procedure will assess participant preference for "today's drug" over various amounts of money ranging from -\$30 (i.e., forego \$30 rather than receive "today's drug") to \$30 (i.e., receive \$30 rather than receive "today's drug").

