Subjective and reinforcing effects of nicotine (e.g., drug liking, take again, monetary value) will be examined as a function of nicotine dose and caffeine maintenance. Repeated measures ANOVAs will be conducted with caffeine maintenance phase (caffeine vs. placebo), drug dose (placebo and 4 doses of nicotine) and time (1, 2, 3, and 4 hours, as appropriate) as within-subjects factors. It is anticipated that there will be a significant drug dose by maintenance phase interaction such that positive subjective ratings on active nicotine sessions will be greater (and more differentiated from placebo) during the caffeine maintenance phase relative to the placebo maintenance phase. A sample size of 11 was previously sufficient to detect significant differences in nicotine reinforcement within subjects as a function of caffeine maintenance in an inpatient study (Jones & [name], 2003). In order to facilitate the exploration of effects of demographics (e.g., age, sex) and previous caffeine use, and to account for additional variability in an outpatient study, we propose a larger sample size of 36. This sample size is consistent with previous outpatient studies conducted by our laboratory that manipulated caffeine maintenance and examined differences in caffeine subjective effects (Evans & [name], 1992). The appropriateness of the proposed sample size is supported by a formal power analysis for repeated measures ANOVA examining an interaction between drug dose (five observations: placebo and four doses of nicotine) and caffeine maintenance (two levels treated as groups in the power analysis, thus conservatively assuming no correlation for this within-subjects factor) assuming an effect size of .20, correlation among repeated measurements of .5, desired power of .8, and $\alpha = .05$.

It is anticipated that in order to have 36 participants successfully complete the study, approximately 60 participants may have to be enrolled in order to allow for the possibility of participant dropout (i.e., attrition of up to 40% of enrolled participants). In order to obtain 60 enrolled participants, we anticipate that as many as 150 individuals may need to be consented and screened for study eligibility during the in-person Screening session (i.e., a screening failure rate of approximately 60%).

d. Early stopping rules.

There are no early stopping rules in this study.

8. Risks

a. Medical risks, listing all procedures, their major and minor risks and expected frequency.

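### The primary ANOVA has no term for session position (1 to 6), so session drift can cost power in the dose-by-phase test if dose order or drift differs between a participant's two phases

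*Combined protocol and SAP*

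**What the plan says.** Section 7.c gives the primary model: "Repeated measures ANOVAs will be conducted with caffeine maintenance phase (caffeine vs. placebo), drug dose (placebo and 4 doses of nicotine) and time". The time factor is defined there as 1 to 4 hours after the capsule, so it does not stand for session number. The predicted result is a dose-by-phase interaction.

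Section 4.b sets six test sessions in each phase. Section 4.a, under the experimental sessions, says: "The order in which the different doses for experimental sessions are received will be counterbalanced across participants". Section 4.c adds that a pharmacy member assigns a randomized dose sequence. Section 4.a also says that the placebo-phase test sessions are run in the same way as the caffeine-phase ones. None of these places says whether one participant receives the same dose order in both phases or a new one. No session drift is mentioned or quantified.

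For sample size, section 7.c says "we propose a larger sample size of 36", with a power analysis "assuming an effect size of .20", "correlation among repeated measurements of .5", power 0.8 and alpha 0.05. Dose has five levels and phase is handled as "two levels treated as groups in the power analysis, thus conservatively assuming no correlation for this within-subjects factor".

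**The concern.** Self-ratings repeated over six sessions may drift, for example through novelty or habituation to the questionnaires. Counterbalancing across participants spreads this drift evenly over doses, so it protects the average dose effects. It does not remove the drift from each participant's own dose contrasts. Without a position term, that variation can only go to error.

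The dose-by-phase test rests on each participant's caffeine-minus-placebo difference at each dose. A drift common to both phases cancels from that difference only if the dose sits at the same position in both. If the order is redrawn, or if drift is stronger in one phase (novelty mainly in the first period, say), the drift stays in the error of the test on which the primary hypothesis depends. What is at stake is power.

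**Working it through.** **Inputs from section 7.c.** Effect size 0.20 (metric not named; read as Cohen's f), correlation rho = 0.5, m = 5 dose levels, k = 2 phases treated as groups, alpha 0.05, target power 0.8, N = 36 completers. **Assumed:** a linear drift totalling D SD from session 1 to session 6.

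**1. The plan's own figure.** For the interaction, lambda = N·m·f²/(1 − rho), with df1 = (k − 1)(m − 1) = 4 and df2 = (N − k)(m − 1).
- N = 32: lambda = 32 × 5 × 0.04/0.5 = 12.8, df2 = 120, power 0.814.
- N = 36: lambda = 14.4, df2 = 136, power 0.864.

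The stated inputs need 32. The plan's 36 exceeds that and meets the target, which agrees with the plan's statement that 36 is supported. Enrolment also reproduces: 36/(1 − 0.40) = 60.

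**2. Variance added by drift when orders differ between phases.** Positions 1 to 6 have variance 35/12 = 2.917. Two doses in the same phase have position covariance −2.917/5 = −0.583. Dose contrasts therefore gain 2.917 + 0.583 = 3.5 times the squared drift per session. With drift D/5 per session, the addition is 3.5 × (D/5)² = 0.14D², against an error variance of (1 − rho) = 0.5 SD².
- D = 0.5: 0.035/0.5 = 7% more error variance.
- D = 1: 0.14/0.5 = 28%.
- D = 2: 0.56/0.5 = 112%.

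**3. Power without a position term.** Put 0.5 + 0.14D² in place of 0.5 in lambda. For 36 participants who complete both phases, N·m becomes 72 × 5.

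| D (SD) | Plan's basis: lambda | Plan's basis: power | 36 full crossovers, f = 0.20: power |
|---|---|---|---|
| 0 | 14.40 | 0.864 | 0.995 |
| 0.5 | 13.46 | 0.837 | 0.993 |
| 0.75 | 12.44 | 0.803 | 0.988 |
| 1 | 11.25 | 0.756 | 0.978 |
| 2 | 6.79 | 0.510 | 0.848 |

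With a 5-df position term, power on the plan's basis stays at about 0.863. Without it, the N needed for 0.8 power rises from 32 to 34, 40 and 66 at D = 0.5, 1 and 2.

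**4. Simulation of the within-subject design** (36 completers, balanced 6 × 6 square, orders redrawn between phases, 1,500 runs, error about 1 point), with a smaller effect, f = 0.14:

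| D (SD) | Without position | With position |
|---|---|---|
| 0 | 0.861 | 0.859 |
| 0.5 | 0.823 | 0.851 |
| 1 | 0.737 | 0.845 |
| 2 | 0.355 | 0.872 |

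**5. Same order in both phases.** With equal drift there is no loss (f = 0.14, D = 2: 0.842 both ways). With drift in the first period only, the loss returns: 0.801 against 0.856 at D = 1, and 0.576 against 0.843 at D = 2 (700 runs, error about 2 points; position fitted by period).

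**6. No true interaction, orders redrawn.** The unadjusted test rejects in 0.036, 0.017 and 0.000 of runs at D = 0.5, 1 and 2. It becomes conservative. The adjusted test stays near 0.05.

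**The case against.** The strongest reply is that the premise is not documented. A reader might infer that any session drift enters the dose-by-phase error, because each dose falls at a different position in each phase. The documents do not say that. They vary order across participants and are silent on a participant's two phases, and if the order is repeated a common drift cancels exactly. This part of the reply stands, so the point must be conditional.

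Second, the size depends on an assumed drift, and at the plan's own effect size the real design has ample power: 36 full crossovers lose about 2 points at 1 SD. That also stands. A material loss needs either the plan's conservative phase-as-groups reckoning or a smaller true effect. A smaller effect is possible, since section 7.a names several primary ratings and no single effect size is assured for all of them.

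Third, a counterbalanced design analysed by repeated-measures ANOVA is an accepted approach, and the unadjusted test is conservative under the null. That is correct: while counterbalancing holds, nothing here shows bias or false positives. Planned attrition of up to 40% may leave positions unevenly spread over doses among completers, but a check with 36 drawn from a balanced 60 gave results similar to full balance. Attrition therefore adds little to the case.

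Finally, position varies between participants at the same dose, so it cannot simply be added as a factor to the stated ANOVA. This is right, and the fix allows for it.

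**Conclusion.** The point holds in conditional form. The primary model omits session position although dose order varies over six sessions per phase. If a participant's order differs between phases, or if drift differs between phases, power is lost in the dose-by-phase test and the estimate stays unbiased while counterbalancing holds.

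The size depends on an assumed linear drift and on reading 0.20 as Cohen's f. A total drift of 1 SD takes the plan's own calculation from above its 0.8 target to below it (0.86 to 0.76). In the real crossover at f = 0.20 the same drift hardly matters. At f = 0.14 it costs about 11 points compared with a model that includes position (0.845 − 0.737 = 0.108). If the order is repeated and drift is equal in both phases, nothing is lost. This is a precision improvement worth making, and it does not call the validity of the planned test into question.

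**What to change.** In section 7.c, specify the primary analysis as a linear mixed model (or an equivalent linear model) with phase, dose, dose by phase and hour, plus categorical session position within phase (1 to 6). Fit position separately for the first and second period if drift may differ between them. Position can be read from the dose sequence that the pharmacy already holds. State in the same section whether each participant's dose order is repeated or redrawn between phases.

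The cost is 5 degrees of freedom, or 10 if position is fitted by period, and a mixed model in place of the plain repeated-measures ANOVA. If there is no drift, almost no power is given up (0.861 against 0.859 at f = 0.14 with the 5-df term). No extra participants or data are needed.

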Examining nicotine reinforcement among non-smokers is particularly important given that nonsmokers would be able to modify their behavior, including their dietary caffeine consumption, to prevent vulnerability to the effects of nicotine and potentially prevent a transition from preliminary exposure to regular smoking. Further, there is growing concern about the appeal of non-combustible tobacco products, such as electronic cigarettes, to people who would not choose to use combustible tobacco products. This may be due in part to the perception that e-cigarettes are safer than smoking (Bhalerao et al., 2019; Sears et al., 2017; Walley et al., 2019). Therefore, studying nicotine reinforcement among non-smokers is timely and may inform vulnerability to both smoking and novel methods of nicotine self-administration. Our laboratory has experience examining the reinforcing effects of oral nicotine among non-smokers under rigorous double-blind conditions (i.e., IRB00165287; Duke et al., 2015). Thus, in the present study, we propose to conduct a within-subjects comparison of subjective and reinforcing effects of nicotine following chronic administration of a moderate daily dose of caffeine relative to a placebo maintenance condition. We hypothesize that healthy individuals will report greater positive subjective and reinforcing effects of oral nicotine during chronic caffeine administration relative to the placebo maintenance condition.

4. Study Procedures

a. Study design, including the sequence and timing of study procedures (distinguish research procedures from those that are part of routine care).

Overview. This double-blind, placebo-controlled study will be conducted over a period of approximately 10-12 weeks. Participation may be longer depending on scheduling considerations. The study will assess participants' subjective ratings of the effects of nicotine (one session each for placebo, 1, 2, 3 and 4 mg/70 kg nicotine) and caffeine (one session of 300 mg caffeine) across two conditions compared within-subjects: a caffeine maintenance condition (4-5 weeks) and a placebo maintenance condition (4-5 weeks). The order in which caffeine and placebo maintenance conditions are administered will be counterbalanced across participants. Figure 1 shows a study overview.

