Final visit. Participants will return to the laboratory to receive their bonus payment for study completion so that we have the opportunity to review their subjective drug effects from the multiplechoice reinforcement session and discuss with them if necessary. They will also complete an end-ofstudy questionnaire which will assess their beliefs about what conditions they may have experienced during the study and any perceived differences between conditions.

Measures

Screening/Descriptive Measures: The following measures will be administered at study screening, the online self-screener or online preliminary screening in order to establish patient eligibility and characterize the sample. Basic demographic information and personality measures will be examined as potential covariates of individual differences in drug response following drug administration. The measures described will be administered via computer or using paper or pencil, and

as such formatting or question wording may change slightly to adjust for computer vs. paper administrations.

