Participants may voluntarily withdraw from the study at any time. They may also be removed if they have a significant adverse effect that we judge likely to be a reaction to a study drug, if they are noncompliant with study procedures or restrictions, if they become pregnant, or if new information becomes available that suggests continued study participation would put them at increased risk of adverse events.

g. Description of what happens to participants receiving therapy when study ends or if a participant's participation in the study ends prematurely.

The proposed study is not a treatment study and participants are healthy volunteers. Neither study participation nor its termination will affect the ability of the participants to seek treatment services. Participants may withdraw from the study at any time without loss of benefits.

5. Inclusion/Exclusion Criteria

Inclusion Criteria

- 1. Participant age is 18-45 years.
- 2. Participant regularly consumes caffeine (e.g., at least once weekly or at least approximately 3 times per month).
- 3. Participant has less than 100 lifetime exposures to tobacco or nicotine-containing products (i.e., accepted definition of a never smoker according to the U.S. Centers for Disease Control).
- 4. Participant has no nicotine use in the last year.
- 5. The subject must be in good health as determined by medical history and vital signs.
- 6. Participant Body Mass Index (BMI) must be between 18.5 and 34.9 (BMI<18.5 = Underweight; BMI>34.9 = moderate-to-high-risk Obese).
- 7. The subject is fluent in English (speaking, writing, and reading) and is capable of understanding and complying with the protocol.
- 8. Females: Females of childbearing potential must agree to use appropriate birth control (barrier methods, hormonal contraceptives, and/or intrauterine devices) during the entire duration of the study. Females who are not of childbearing potential must be postmenopausal for 2 years or have a history of hysterectomy and/or oophorectomy.

Exclusion Criteria

- 1. Subjects with known hypersensitivity or medical contraindication to the study drugs.
- 2. Subjects with a significant current neurological, hepatic, renal, endocrine, cardiovascular, gastrointestinal, pulmonary or metabolic disease for which administration of the study drugs would be contraindicated.

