Both study drugs to be administered are legally marketed in the United States. Further, the study does not involve a route of administration, dose, or patient population that significantly increases the risk (or decreases the acceptability of the risk) associated with the use of the drug. Previous research has demonstrated that caffeine (Sigmon & [name], 2011) and nicotine (Duke et al., 2015) at the proposed doses (or indeed at higher doses) and the proposed route of administration (oral) are well-tolerated in non-drug-abusing volunteers. The maximum study dose of nicotine is consistent with what is currently available over-the-counter in oral form (e.g., 4 mg lozenges or gum). Caffeine is readily available over-the-counter in medications, supplements, beverages, and foods. The study is not intended to be reported to FDA in support of a new indication or to support any other change in labeling of the drugs. The study does not intended to promote or commercialize the drug products. As such, the proposed investigation is exempt from IND requirements because all of the criteria for an exemption in FDA regulations § 312.2(b) are met.

c. Justification and safety information if non-FDA approved drugs without an IND will be administered.

N/A

7. Study Statistics

a. Primary outcome variable.

Primary outcome measures will be participant ratings assessed pre-drug and at 1, 2, 3, and 4 hours post capsule administration during the experimental test sessions examining placebo, nicotine, and caffeine. Primary outcomes include subjective ratings (e.g. Subjective Effects Questionnaire, and surrogate measures of reinforcement such as liking, take again, monetary value). Primary outcomes will be compared within-subjects across the caffeine maintenance condition and the placebo maintenance condition.

b. Secondary outcome variables.

Secondary outcome measures will be subject demographic characteristics, drug use history, personality factors (e.g., sensation seeking), and decision-making factors (i.e., delay discounting) that will be examined as they correlate to positive subjective effects of nicotine during the experimental test sessions.

c. Statistical plan including sample size justification and interim data analysis.

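### Maintenance order is counterbalanced but absent from the planned ANOVA: adding it is a cheap gain in precision for the overall phase contrasts and matters little for the predicted dose-by-phase interaction

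*Combined protocol and SAP*

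**What the plan says.** Section 4.a (Overview) sets up the crossover: "The order in which caffeine and placebo maintenance conditions are administered will be counterbalanced across participants". Each maintenance condition lasts 4-5 weeks, with about one week between them. Section 7.a makes the comparison of the two conditions the primary one: "Primary outcomes will be compared within-subjects across the caffeine maintenance condition and the placebo maintenance condition".

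Section 7.c gives the model: "Repeated measures ANOVAs will be conducted with caffeine maintenance phase (caffeine vs. placebo), drug dose (placebo and 4 doses of nicotine) and time", the last entering as "time (1, 2, 3, and 4 hours, as appropriate) as within-subjects factors". The result it anticipates is a drug dose by maintenance phase interaction.

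Order would be a between-subjects factor, and no section adds order, period or sequence to any analysis. The between-person variables that are named serve another purpose. Section 7.c justifies the larger sample partly "In order to facilitate the exploration of effects of demographics (e.g., age, sex) and previous caffeine use", section 4.a (Measures) says "Basic demographic information and personality measures will be examined as potential covariates of individual differences in drug response", and section 7.b adds drug use history and delay discounting.

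The target is 36 completers from about 60 enrolled, allowing for "attrition of up to 40% of enrolled participants". No split by order is stated for either number.

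**The concern.** Counterbalancing spreads a period effect evenly over the two conditions; it does not remove it from the data. Suppose ratings drift between the first and second phase. Then caffeine-minus-placebo differences are raised in one order and lowered in the other. Without an order term, that spread is counted as random variation between people. The phase test becomes conservative and loses power. If the orders end up unequal among completers, part of the drift also enters the estimate.

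Drift is plausible. Participants rate themselves repeatedly over 12 experimental sessions. Inclusion criterion 4 reads "Participant has no nicotine use in the last year", yet each participant takes four active nicotine doses in the first phase and repeats them in the second. The documents give no size for an overall drift or for one that differs by dose.

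**Working it through.** **The plan's own figures.** Attrition reproduces: 36/(1 - 0.40) = 60. For the power statement I read the effect size of .20 as Cohen's f, with five dose observations, correlation .5 and the two maintenance levels as groups. The noncentrality is f² x N x 5/(1 - 0.5) = 0.04 x 36 x 5/0.5 = 14.4 on 4 and 4 x (36 - 2) = 136 df, so power is 0.864. N = 32 already gives 0.814. The plan says only that the analysis supports 36, so this is no error.

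**Model for an overall phase contrast.** Let each participant's caffeine-minus-placebo difference be

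D = effect + p x s + noise,

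with s = +1 for placebo first, s = -1 for caffeine first, and noise SD 1. Here p is the second-minus-first-phase shift in SDs of D. From the documents: 36 completers and alpha .05. Assumed: a true effect of 0.5, p from 0 to 0.5, a two-sided test, and an even 18/18 split.

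- Error variance without the term at 18/18 is multiplied by 1 + p² x 36/35: 1.064 at p = 0.25 and 1.257 at p = 0.5. In completers, 36/1.064 = 33.8 and 36/1.257 = 28.6.
- Power with the term uses a noncentral t on 34 df with effective N = 4 x n1 x n2/36.
- Power without it uses exact integration over the inflated residual sum of squares on 35 df.

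| p (18/18) | Power, no term | Power, with term | Null rejection, no term |
|---|---|---|---|
| 0 | 0.831 | 0.830 | 0.050 |
| 0.25 | 0.814 | 0.830 | 0.044 |
| 0.5 | 0.763 | 0.830 | 0.029 |

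**Uneven completers.** The estimate without the term shifts by p x (n1 - n2)/36. At 21/15 this is 6/36 = 0.17 of the period effect. With p = 0.5, power without the term is 0.886 or 0.594 depending on the direction of the imbalance, against 0.820 with it. Assume 30 enrolled per order and dropout unrelated to order. The hypergeometric probability of 18/18 is then 0.21, of 21/15 or worse 0.19, and of 24/12 or worse 0.003. The shift averages to zero over these splits. Average power without and with the term is 0.831 and 0.826 (p = 0), 0.812 and 0.826 (p = 0.25), and 0.753 and 0.826 (p = 0.5). The two are equal at about p = 0.13.

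**The predicted dose-by-phase interaction.** Each phase has its own placebo session, so a period shift common to all doses cancels: in simulation the interaction error mean square stays at 1.00 and power at 0.86 with or without the term. Only a dose-by-period effect enters. For the 4-df F test, with a linear dose trend calibrated to 0.80 power with the term at 18/18:

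| Dose-by-period effect relative to true interaction | No term | With term |
|---|---|---|
| none | 0.80 | 0.80 |
| half | 0.79 | 0.80 |
| equal | 0.76 | 0.80 |

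Averaged over chance splits, power without and with the term is 0.801 and 0.795 (none), 0.798 and 0.796 (one quarter), 0.790 and 0.797 (half), and 0.747 and 0.795 (equal). The term starts to pay once the dose-by-period effect lies between a quarter and a half of the true interaction.

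**The case against.** The strongest reply is that the larger losses belong to a test the plan neither predicts nor powers. Section 7.c anticipates the dose-by-phase interaction, where a common period shift drops out. What remains needs a dose-by-period effect that nothing in the documents sizes, and if it is small the term costs a little power on average. All of this stands.

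A second reply is that calibrating to 0.80 removes a margin the plan may have. All 36 completers supply both phases. Under the plan's own inputs and no correlation between phases, the noncentrality doubles from 14.4 to 28.8 and power is about 0.995. A dose-by-period effect equal to the interaction would then lower it only to about 0.99. That is right if .20 is the true effect, and it makes the interaction loss smaller still.

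Third, the design already protects: dose order is counterbalanced too, the pharmacy assigns randomized dose sequences, and each phase opens with at least a week of maintenance before testing. These limit confounding of phase with time. They do not take period variance out of the error for phase contrasts, and section 7.a does compare outcomes across the phases.

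A reader might infer that the main hypothesis test is biased, or that all period variance sits in its error term. The documents support neither. With even orders the phase test is conservative, chance imbalance averages out, and the interaction is immune to a common shift.

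**Conclusion.** The omission is real, and its consequence is modest. For overall phase contrasts, leaving order out costs power if ratings drift between phases: 0.83 to 0.81 at an assumed 0.25 SD and to 0.76 at 0.5 SD, the latter equivalent to about 29 completers instead of 36. An uneven split can also move a single trial's estimate by the imbalance fraction of the period effect. For the predicted interaction the loss is 0.01 to 0.04 when a dose-by-period effect is half of, or equal to, the true interaction, and nil under a common shift.

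The true effect of 0.5 SD, every period-effect size, the 18/18 completers and the 30/30 enrolment are assumptions. This is an improvement in efficiency and precision worth considering, not a flaw that undermines the trial's conclusions.

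**What to change.** In section 7.c, prespecify maintenance order (caffeine first or placebo first) as a between-subjects factor with its phase and dose-by-phase interactions. Test phase and dose-by-phase with the two orders weighted equally (Type III). Order-by-phase then carries the period effect and order-by-dose-by-phase the dose-by-period effect. Report enrolment, attrition and exclusions by order. As a minor option, the pharmacy could assign each replacement to the order of the participant who dropped out.

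No new data are needed, since the allocation is already assigned. The cost is 1 error degree of freedom per contrast (35 to 34; 140 to 136 for the 4-df test, the same 136 as in the reading of the plan's power model above). If there is no period effect, average power falls by about 0.005. For the phase contrast, power with the term is 0.820 at 21/15 and 0.785 at the improbable 24/12, against 0.831 without it. The term does not correct selection from dropout that differs by order, which is why attrition by order should be shown.
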